3. STUDY DESIGN

This is a randomized, multicenter, parallel-group trial to determine whether a 12-week group-based yoga intervention is effective in decreasing the frequency and impact of urinary incontinence in middle-aged and older women. Women aged 45 years and older who document at least daily episodes of stress-, urgency-, or mixed-type incontinence on a screening voiding diary, are not using other clinical treatments for incontinence, and meet minimum physical mobility requirements and other eligibility criteria will be recruited from multiple locations in northern California by coordinators affiliated with the University of California San Francisco or Stanford University. Eligible women will be randomized in a 1:1 ratio to participate in either a 12-week yoga program (N~120) or a time-equivalent, non-specific muscle stretching and strengthening control program (N~120).

Women randomized to the yoga program will take part in twice weekly group yoga classes involving an expected 8 to 12 other women as well as practice study-specific yoga techniques at home for at least one hour per week for a total of 12 weeks. Women randomized to the muscle stretching and strengthening (a.k.a physical conditioning) control group will take part in twice weekly group physical conditioning classes and practice physical conditioning exercises at least one hour per week at home for 12 weeks. During the 12- and 24-week post-intervention follow-up period, participants will also be encouraged to continue practicing yoga or stretching/strengthening exercises for at least two hours per week.

To address objective 1, we will use validated voiding diaries to examine changes in frequency of total incontinence during the 12-week intervention, as well as explore persistence of effects on incontinence frequency after the end of the intervention programs. To address objective 2, we will further examine changes in frequency of different clinical types of incontinence as well as daytime and nighttime incontinence during the 12-week intervention, as well as the post-intervention follow-up periods. To address objective 3, we will analyze data from validated questionnaires in order to examine changes in incontinence-related functioning and quality of life over these same time periods. To address objective 4, we will assess changes in pelvic floor strength assessed during pelvic exam, autonomic

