Staff qualifications and training: Each yoga class series will be led by a primary instructor who must: 1) have at least 2 years of experience teaching yoga in the community; 2) review a detailed, study-specific written instructor manual describing all of the postures and yoga techniques to be used in the study program; 3) complete at least 2 hours of in-person training in study-specific yoga techniques with one of the study yoga expert consultants; 4) complete additional study-specific training in clinical trial procedures, documentation of participant attendance, review of home practice logs, and recording of yoga postures practiced during group classes on appropriate study forms; 5) carry and submit proof of personal liability insurance (minimum of \$2 million coverage); and 6) confirm his or her willingness to adhere to the study intervention procedures. For each class series, a back-up instructor will also be identified who can teach a class in the event that the primary instructor is ill or is unable to teach due to an emergency.

Orientation and classes: Prior to group instruction, participants in each class series will attend a 90-minute group orientation led by the appointed class instructor. This will include an overview of the general principles of Iyengar/alignment yoga, an orientation to the structures of the pelvis, spine, and lower extremity, and an introduction to the postures to be practiced and the props to be used in the study. After the orientation, women will attend 90-minute group classes twice weekly for 12 weeks, led by the same instructor. For classes with 10 or more students, the instructor may be supported by an assistant who will help to provide personalized attention to students. During group classes with no more than 15 participants, the instructor will guide women in practicing yoga postures, calling attention to ways in which postures can improve pelvic floor function and adapt postures to accommodate physical limitations. Women will also be taught to avoid habits that may worsen incontinence during practice, such as squeezing of abdominal rather than pelvic muscles. Following a study-specific guide, instructors will gradually

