Staff qualifications and training: Each stretching/strengthening class series will be led by a primary instructor who: 1) is either certified as a personal trainer through the National Academy of Sports Medicine, National Strength and Conditioning Association, or the American College of Sports Medicine, or National Strength and Conditioning Association (NSCA), or licensed as a physical therapist by the Physical Therapy Board of California; 2) has at least 2 years of experience working as a physical therapist or physical trainer in either individual or group settings; 3) will have reviewed a detailed, study-specific training manual describing all of the stretching/strengthening exercises to be used in the study program; 4) will have completed at least 2 hours of in-person training in study-specific techniques with study expert consultant; 5) will have completed additional study-specific training in clinical trial procedures, documentation of participant attendance, review of home practice logs (for adherence), and recording of exercises performed during group classes on appropriate study forms; 6) carries and submits proof of personal liability insurance (minimum of \$2 million coverage); 7) confirms his or her willingness to adhere to the study intervention procedures. For each class series, a back-up instructor will also be identified who can teach a class in the event that the primary instructor is ill or is unable to teach due to an emergency.

Group orientation and classes: Similar to the yoga program, the stretching/strengthening control program will begin with a group orientation led by a physical therapist/trainer, who will provide an overview of the stretching/strengthening exercises to be covered in the program. This will be followed by 90-minute twice weekly group classes, each with no more than 15 participants, led by the same therapist/trainer, who will have received in-person study-specific training from a study expert physical therapist consultant. Classes will be designed to make women comfortable with all exercises by 6 weeks and fully confident in performing exercises by 12 weeks. During the COVID-19 pandemic, classes may be converted to remote platforms (i.e., may take the form of interactive on-line video-based classes rather than in-person classes).

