9.6 Data Analyses

9.6.1 Analyses to address main objectives

Objective 1: To determine the efficacy of a group-based yoga intervention in reducing the frequency of urinary incontinence in ambulatory midlife and older women.

Hypothesis 1A: Ambulatory incontinent women randomized to the yoga intervention will demonstrate at least a 20% greater decrease in total incontinence frequency (measured by validated voiding diaries) over 12 weeks, compared to women randomized to the control intervention.

Hypothesis 1B: If improvements in total incontinence frequency are observed at 12 weeks, these improvements will be sustained 12 and 24 weeks after the end of the intervention programs.

Planned analyses: Intervention effects on the primary outcome of total incontinence frequency will be estimated using a linear mixed model (LMM) for changes since baseline in the overall frequency of any incontinence episodes at 6 and 12 weeks, adjusting for baseline incontinence frequency. Analyses will be by intention to treat, according to intervention group assignment, and without regard to adherence to intervention classes or practice. The LMM will account for clustering using nested random effects for group intervention class series and individual participant. In addition to fixed effects for study location and type of incontinence, the LMM will include terms for intervention, time, and the time-by-intervention interaction, thus allowing for secular trends in controls, as well as different intervention effects at 6 and 12 weeks. The intervention effect will be summarized by an orthogonal contrast capturing any linear trend across 6 and 12 weeks; this makes use of information for participants with 6 but not 12 week outcomes. If the yoga intervention appears effective over 12 weeks, we will also assess maintenance of effects over time, by comparing changes since baseline at 12 weeks with those at 24 and 36 weeks, using an additional LMM. Intervention effects will again be summarized by an orthogonal contrast for linear trend across the three time points.

Objective 2: To determine the efficacy of a group-based yoga intervention in reducing the frequency of type- and context-specific urinary incontinence in ambulatory middle-aged and older women.

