Planned analyses: Additional intermediary outcomes include pelvic floor muscle strength (measured by Brink scale), peripheral autonomic function (reflected by respiratory sinus arrhythmia [RSA] and cardiac pre-ejection period [PEP] parameters), and lower extremity physical function (assessed using the Short Physical Performance Battery [SBBP] and 2-minute step test). Intervention effects will first be estimated using LMMs, using the same modeling strategy used for objectives 1-3. Next, to assess for mediation of changes in incontinence frequency by changes in these factors, we will assess correlation between changes in these

parameters and change in incontinence frequency between baseline and 12 weeks. We will then examine attenuation of intervention effects estimates from the primary intention-to-treat analyses after adjustment for these potential mediators. Mediators will initially be analyzed as continuous variables (i.e., continuous change in RSA and PEP), but categorization will be considered in the event of skewed variable distributions. If evidence of mediation is observed, we will estimate 95% bias-corrected percentile confidence intervals for the proportion of intervention effect explained, using resampling by participant to fully account for the correlation between intervention effect estimates before and after adjustment for change in the mediators

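### The bootstrap interval for the proportion of effect explained leaves out the class-series level of the plan's own model, and will be too narrow if incontinence outcomes cluster by class series

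*Combined protocol and SAP*

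**What the plan says.** All references are to the combined protocol and SAP.

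- **Primary model (9.6.1, Objective 1).** "The LMM will account for clustering using nested random effects for group intervention class series and individual participant".
- **Objective 4 (9.6.1).** Intervention effects on the potential mediators are estimated "using the same modeling strategy used for objectives 1-3". Mediation is then judged by how far the primary intention-to-treat effect shrinks once change in the mediator is added.
- **The resampling unit (9.6.1, Objective 4).** The bootstrap draws single women: "using resampling by participant to fully account for the correlation between intervention effect estimates before and after adjustment for change in the mediators".
- **What the bootstrap is for (same place).** It serves one quantity: "we will estimate 95% bias-corrected percentile confidence intervals for the proportion of intervention effect explained". This step is taken only under a condition: "If evidence of mediation is observed".
- **Class size.** Section 3 has "group yoga classes involving an expected 8 to 12 other women". The ceilings are "During group classes with no more than 15 participants" for yoga (5.1) and "each with no more than 15 participants, led by the same therapist/trainer" for control (5.2).

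No section mentions resampling class series, and none gives an ICC for them.

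**The concern.** The model has two levels of dependence, the woman and her class series, but the bootstrap redraws only the first. Each series belongs to one arm, so the intervention effect is a contrast between sets of series. Its uncertainty includes how the series happened to turn out. Redrawing women from the same observed series leaves almost all of that out, and refitting the mixed model in each draw does not restore it, because percentile limits come from the spread of the draws.

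Variation between series is plausible on the plan's own description. One instructor leads each series (5.1, 5.2), yoga participants are encouraged to practise with classmates (5.1), recruitment runs in waves (4.3), and some waves may be taught remotely (9.6.2).

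This interval is the only measure of uncertainty named for the proportion explained. If it is too short, a mechanism looks more precisely established than it is.

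**Working it through.** **1. The plan's own figure.** Objective 4 states no number, so the only figure to reproduce is the sample size in 9.2.
- Difference: 0.20 × 23 = 4.6 episodes/week. SD after baseline adjustment: 14.4 × √(1 − 0.59²) = 11.63.
- n per arm = 2 × (1.960 + 0.842)² × 11.63² / 4.6² = 100.3, so 101. With 15% loss, 101/0.85 = 118.8, so 119 per arm and 238 in total, against the stated 240.

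This reproduces the plan without any allowance for class series, so no class-series ICC can be inferred from it.

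**2. Number of series.** Eight to 12 other women means 9 to 13 per class. 120/13 = 9.2 and 120/9 = 13.3, so about 9-13 series per arm. Completers: 0.85 × 120 = 102 per arm, or 8.5 per series with 12 series.

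**3. What resampling women loses.** For an arm mean with k series of m women, between-series variance B and within-series variance W:
- true variance: B/k + W/(km)
- variance seen by participant resampling: (B + W)/(km)
- ratio: 1 + (m − 1) × ICC

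The between-series part is divided by the number of women instead of the number of series. The target here is a ratio, (unadjusted effect − adjusted effect)/unadjusted effect, so its interval has to be checked by simulation.

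**4. Simulation.** Assumptions not in the documents: ICC equal in outcome and mediator, 12 series per arm, least-squares attenuation standing in for the mixed model. Limits are bias-corrected percentile.
- A: 8 women per series, true proportion 0.5, total effect 0.40 SD, 1200 trials × 600 draws; series resampling takes k − 1 of k.
- B: 8.5 women per series, true proportion 0.30, total effect 4.7, residual SD 11.63, mediator shift 0.5 SD, 1000 trials × 1000 draws; series resampling takes all k.
- C: 8 women per series; series resampling takes k − 1 of k.

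Coverage (%) of the nominal 95% interval for the proportion explained, participant / series resampling:

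| Assumed ICC | A | B | C |
|---|---|---|---|
| 0 | – | 95.0 / 93.5 | 94.7 / 94.7 |
| 0.02 | 94-95 / 95 | 93.7 / 93.7 | 93.8 / 94.1 |
| 0.05 | 92-93 / 93.5 | 92.0 / 93.6 | 92.6 / 93.7 |
| 0.10 | 90 / 93 | 89.0 / 91.8 | 88.8 / 90.9 |

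Monte Carlo error is about 0.7-1 point per entry.

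Median widths in B, participant / series:
- ICC 0: 0.841 / 0.777
- ICC 0.02: 0.850 / 0.861
- ICC 0.05: 0.835 / 1.001 (17% narrower)
- ICC 0.10: 0.845 / 1.316 (36% narrower)

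The participant width hardly moves as clustering grows.

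**5. Which clustering matters (set-up B, ICC 0.05 in one variable only).**
- Outcome only: participant width 0.83 against 0.98 for series resampling; participant coverage 92.4%.
- Mediator only: 0.85 against 0.80; participant coverage 95.3%, so the interval is not too narrow.

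**The case against.** **The result is conditional.** This stands. The only ICC in the documents, 0.4-0.8 in 9.2, belongs to the power statement for secondary outcomes and reads as a correlation between repeated values. As a class-series ICC, even 0.4 would give a design effect of 1 + 7.5 × 0.4 = 4.0. That would double the 0.392 SD detectable with 102 per arm (no baseline adjustment) to about 0.78 SD, far outside the plan's 0.26-0.39. A reader might infer that the interval is too narrow as a matter of fact. The documents do not support that: at ICC 0 to 0.02 there is no material shortfall.

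**The design effect overstates the size.** A reader might take √(1 + 7 × 0.05) = √1.35 = 1.16 and say the interval should be 16% wider. That factor applies to the intervention effect itself. The plan estimates that effect with the nested mixed model and plans no bootstrap interval for it.

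**The plan makes no false claim.** A reader might take the completeness claimed in 9.6.1 to cover correlation among classmates. It refers only to the correlation between the two effect estimates, which participant resampling does capture. The fair criticism is a missing variance component.

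**Fewer women may have mediator data.** Pelvic floor assessment is optional (6.1.7), and autonomic measures could be declined during the pandemic (6.1.6). If half had data (an assumption; m = 4), the design effect at ICC 0.05 is 1 + 3 × 0.05 = 1.15 instead of 1.35. This weakens the point for those mediators but does not remove it.

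**The stakes are limited.** The analysis is exploratory and conditional, and its interval is already wide (about 0.84 on the proportion scale in B). This argues for low severity. It does not reconcile the two parts of 9.6.1.

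**Conclusion.** The point holds as a conditional inconsistency of minor severity. The plan accepts class series as a level of dependence, then builds one interval as if that level were absent. Whether this matters depends on the class-series ICC of the incontinence outcome. The coverage loss is negligible at 0.02, about 2 to 3 points at 0.05, and about 5 to 6 points at 0.10. The gain from resampling series is about 0.5 to 1.6 points at 0.05, close to simulation error, and 2 to 3 points at 0.10.

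These sizes rest on assumed ICCs, about 12 equal series per arm, 8 to 8.5 evaluable women in each, and a least-squares stand-in for the mixed model. The primary test, the sample size and the efficacy conclusions are not touched.

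**What to change.** In 9.6.1, Objective 4, make the class series the resampling unit in place of the participant. In each draw:
- sample whole series with replacement separately within each arm, with a small-cluster correction such as k − 1 of that arm's k series;
- keep all visits of each woman together;
- refit both the unadjusted and the mediator-adjusted model.

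A parametric bootstrap from the nested mixed model is an acceptable alternative. Add a sentence saying that, with about 9-13 series per arm, coverage may still fall somewhat below 95%.

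The cost is one or two sentences and a changed resampling index. The downside is wider intervals when outcomes do cluster. If they do not, little is lost: at ICC 0 the k − 1 scheme covered 94.7%, the same as participant resampling. The correction is partial, with 90.9% to 93% coverage at ICC 0.10 under the k − 1 scheme.

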9.6.2 Other analytic issues

Participant dropout (i.e., early termination or loss-to-follow-up). Participant dropout levels are expected to be <15% at 12 weeks of intervention, <20% at 12 weeks post-intervention follow-up, and <25% at 24 weeks post-intervention follow-up, assuming a similar rate of attrition over time. The assumption of non-informative dropout will be assessed by comparing baseline characteristics and early post-randomization outcomes of dropouts vs. non-dropouts. If dropout rates differ between groups, sensitivity analyses to evaluate the effects of participant dropout on estimates of intervention effects may be run using inverse probability of retention weights, which can legitimately include post-randomization variables associated with dropout. Alternately or in addition to this, we may use multiple imputation of missing outcomes under plausible informative missingness assumptions.¹⁰⁴

Dose effects (length of exposure and intensity of practice). In the event that the primary analysis shows that yoga intervention is effective in reducing incontinence frequency over 12 weeks, we may use a closed test procedure to assess for dose response in length of intervention exposure without inflating type-I error.¹⁰⁵ Specifically, if we detect a statistically significant benefit over 12 weeks an alpha of 0.05, we may assess change from baseline to 6 weeks, and from 6 weeks to 12 weeks, also at alpha of 0.05, based on contrasts that can be obtained from the primary analysis model. In exploratory analyses, we may also examine whether cumulative hours spent in group intervention classes (based on class attendance logs), or total hours of home yoga or stretching/strengthening practice (documented by participants' home practice logs), are associated with changes in incontinence frequency or secondary outcomes in each group. After the end of the 12-week intervention, additional exploratory analyses may examine associations between continued yoga or control intervention practice (based on continued home practice hours) and maintenance of intervention effects.

Exploratory subgroup analyses. Intervention effects will be analyzed in subgroups in multivariate analysis based on a limited set of clinicopathologic factors that are hypothesized to have the potential to influence participants' response to the yoga and stretching/strengthening interventions. For example, we may explore whether baseline participant age, race/ethnicity, clinical type of incontinence, pelvic floor muscle strength, or physical function levels influence subsequent treatment-associated changes in primary and secondary outcomes. Subgroup-specific effects, estimated using the interaction model, will be presented only if the interaction between treatment and subgroup is statistically significant at $p < 0.05$.

During the COVID-19 pandemic, intervention instruction in some study waves may be converted to remote platforms (i.e., interactive video-based class instruction rather than in-person class instruction). In that event, we will use the methods outlined above for exploratory subgroup analyses to evaluate differences in the effect of the intervention in waves that rely primarily on video-based instruction rather than in-person instruction.

Co-intervention effects. Because awareness of intervention assignment can affect use of co-interventions, women in both groups will be asked to refrain from using other clinical incontinence treatments during the study. Nevertheless, information about co-interventions will be collected at follow-up visits to permit assessment of potential effects of differential use of co-interventions on outcomes. To estimate the direct effect of the intervention in the absence of co-interventions, we may conduct additional analyses to add co-intervention use, as well as confounders of its effect on the outcome, to the primary treatment model; if factors that are also affected by the co-interventions are among the confounders, we may use inverse weighting rather than direct adjustment for this purpose.

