5.3.2 Prohibited or Discouraged Interventions

Participants will be asked to refrain from using other standard clinical treatments for incontinence during the 12-week intervention period. These include medications with the potential to affect incontinence (anticholinergic bladder medications, tricyclic antidepressants, mirabegron), invasive or surgical bladder treatments, nerve stimulation therapy, medical devices used to improve bladder symptoms (e.g., pessary), and behavioral treatment programs administered by certified practitioners (e.g., pelvic floor rehabilitation therapy, biofeedback programs).

Participants will be queried about use of these treatments at baseline, at the 6-week and 12-week clinic visits. If participants are found to be using these treatments during the 12-week study intervention period, they will not be required to terminate the study early, but use of outside treatment will be recorded as a protocol deviation, and information about use of these additional treatments may be taken into account in per protocol data analyses.

During the 12- and 24-week post-intervention follow-up periods, participants will also be encouraged to avoid using other clinical treatments for incontinence, and instead focus on continued home practice of study yoga or muscle stretching/strengthening exercises to manage their symptoms.

Participants will be queried about use of these treatments at the 12- and 24-week follow-up assessments, so that information about use of these treatments can be incorporated into data analyses. However, use of other clinical incontinence treatments during the 12- and 24-week post-intervention follow-up periods will not be considered a protocol deviation.

Additionally, participants will be asked to refrain from starting or changing the dosage of medications that could affect depression or anxiety symptoms (e.g., antidepressants, sedatives/hypnotics, or antipsychotic agents) during the 12-week intervention period or 12- or 24-week post-intervention follow-up period, although maintenance of stable dosages of these medications will be acceptable.

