9.5 Outcomes

9.5.1 Primary Efficacy Outcome

The primary efficacy outcome will be change in the average frequency of any urinary incontinence over 12 weeks based on a validated 3-day voiding diary. To that end, frequency of incontinence will be assessed based on voiding diaries completed at screening/baseline, 6 weeks, and 12 weeks. If improvement in incontinence is observed over 12 weeks, additional analyses may explore persistence of benefits 12 and 24 weeks after the completion of the yoga or stretching/strengthening programs.

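### The trigger for inverse weighting in the optional co-intervention analysis omits confounders changed by assignment, so the estimated direct effect of yoga could be biased, most likely toward understatement

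*Combined protocol and SAP*

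**What the plan says.** The paragraph on co-intervention effects in section 9.6.2 starts from the fact that participants are not blinded: "awareness of intervention assignment can affect use of co-interventions". It states its target: "To estimate the direct effect of the intervention in the absence of co-interventions". The default method is to "add co-intervention use, as well as confounders of its effect on the outcome, to the primary treatment model". The alternative is conditional and optional: "if factors that are also affected by the co-interventions are among the confounders, we may use inverse weighting rather than direct adjustment". The paragraph lists no confounders and does not mention confounders affected by the assigned intervention.

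Other sections bear on this:

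- Section 5.3.2, on outside treatments: "Participants will be queried about use of these treatments at baseline, at the 6-week and 12-week clinic visits".
- Section 9.5.1, on the primary outcome: "frequency of incontinence will be assessed based on voiding diaries completed at screening/baseline, 6 weeks, and 12 weeks".
- Section 9.6.1: the primary mixed model takes the 6- and 12-week changes as joint outcomes and allows "different intervention effects at 6 and 12 weeks".
- Section 9.6.2, on dropout, contemplates "inverse probability of retention weights, which can legitimately include post-randomization variables associated with dropout".

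**The concern.** The target is a controlled direct effect: assignment is the exposure and co-intervention use is the intermediate. Suppose a variable confounds the link between co-intervention and outcome, and assignment also changes it. That variable then carries part of yoga's own effect. Entering it as a covariate removes that part, although it has nothing to do with outside treatment. The usual remedy is to put the variable in a weight model for co-intervention use and leave it out of the outcome model.

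The 6-week frequency fits this description. The plan allows an intervention effect on it, women still leaking at 6 weeks are plausibly those who seek other treatment, and it predicts week 12. If it is not also affected by co-interventions, the stated condition is not met and the default is direct adjustment.

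Readers would turn to this analysis to rule out differential outside treatment in an unblinded trial. If its estimate is too small, they may credit outside treatment with part of yoga's benefit.

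**Working it through.** **Scale of the inputs.** The plan gives no figure for this analysis, so the inputs come from section 9.2: baseline about 23-24 episodes/week, difference 20%, SD of change 14.4, correlation 0.59, loss 15%, N = 240. Using the correlation to remove baseline variance gives a residual SD of 14.4 × √(1 − 0.59²) = 11.63. With a difference of 0.20 × 23 = 4.6, 80% power and two-sided 5%, this needs 101 per arm. Then 101/0.85 = 118.8, rounded up to 119 per arm, or 238 in all, which agrees with 240. This depends on how the 0.59 is used: the raw SD of 14.4 gives 336 to 364. The week-12 effect below is 0.20 × 23.5 = 4.7, that is -4.7 episodes/week.

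**Bias from direct adjustment at week 12.** Let δ be the effect of assignment on 6-week frequency and r the correlation of 6- and 12-week frequency after baseline adjustment, with equal residual SDs at the two times. The assignment coefficient after entering the 6-week value is approximately -4.7 − r × δ.

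Both δ and r are assumptions. Section 9.2 does not say which time points its 0.59 links. Taking it as the baseline-adjusted value gives r = 0.59. If it holds between every pair of times, the baseline-adjusted value is (0.59 − 0.59²)/(1 − 0.59²) = 0.59/1.59 = 0.37.

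| δ | r = 0.37 | r = 0.59 |
|---|---|---|
| -2 | -3.96 (16% too small) | -3.52 (25%) |
| -3 | -3.59 (24%) | -2.93 (38%) |
| -4 | -3.22 (32%) | -2.34 (50%) |

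A large simulation at r = 0.59 agrees. It assumed that 10-12% of women use outside treatment and that this lowers frequency by 5/week. Direct adjustment gave -3.50, -2.93 and -2.36. Weighting gave -4.69 to -4.72, and plain intention-to-treat gave about -4.6. So in this setting co-interventions moved the estimate by about 0.1, while direct adjustment moved it by 1.2 to 2.3.

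**Which confounders cause the bias.** A second simulation, with stronger assumed paths and an unmeasured cause shared by the interim value and the outcome, separated the cases. The true direct effect was -4.70.

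| Confounder affected by | Plan's condition | Direct adjustment | Weighting |
|---|---|---|---|
| assignment only | not met | -1.15 | -4.65 |
| co-intervention only | met | -4.72 | -4.69 |
| both | met | -1.15 | -4.67 |

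The effect of assignment on the confounder is what biases direct adjustment here. With assignment effects on the confounder of -1 to -4.7 and confounder-to-outcome slopes of 0.25 to 0.75, direct adjustment recovered 1% to 90% of the direct effect. Rare use does not help: with 3% use it gave -1.17. When assignment worsened the confounder, the direction reversed (-6.21).

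**The case against.** **The existing condition may be met anyway.** It has no time limit. Section 5.3.1 gives both arms self-management techniques at baseline and treats their use as co-intervention, and use is recorded at 6 weeks. Use in weeks 0-6 could affect the 6-week diary, which opens the way to weighting. This stands, so the bias is not certain. But weighting would still be only a possibility, and it would be reached for a reason other than the one that matters for this target.

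**The plan names no confounders and never proposes the 6-week diary as a covariate.** That is correct. An analyst who used baseline confounders only would not meet this bias, and the text permits that. The 6-week diary is also an outcome in the primary mixed model, so the percentages above describe a week-12 regression with the 6-week value as a covariate, not the documented model and its trend contrast. What stands against the plan is that nothing in the paragraph steers the analyst away from this choice.

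**A reader might infer that the condition is simply wrong.** The documents do not support that. Confounders affected by earlier co-intervention use are the usual reason for weighting when a time-varying co-intervention is the exposure. The condition is incomplete and should be kept and extended.

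**Conclusion.** The point holds as a gap in an optional, supplementary analysis. For the stated target, confounders changed by assignment invalidate direct adjustment, and the condition for weighting does not cover them. If such a confounder is entered as a covariate, the direct effect is biased. Understatement is most likely if yoga improves the confounder, as the trial's hypotheses imply.

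The size, roughly 16% to 50% too small, rests on a week-12 effect of -4.7, a 6-week effect of -2 to -4, a baseline-adjusted correlation of 0.37 to 0.59 and equal residual SDs. The documents give none of these path strengths, and other assumptions give a wider range.

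A reader might go on to conclude that the analysis as written will understate yoga's effect, or that the trial's main result is in doubt. Neither follows. Direction and size are conditional, and the primary intention-to-treat analysis and the sample size of 240 are untouched. This is a cheap improvement.

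**What to change.** In section 9.6.2, replace the condition with: *if any confounder is measured after randomisation and may be affected by the assigned intervention or by earlier co-intervention use, inverse weighting will be used and such variables will not be entered as covariates; direct adjustment will be used for baseline confounders only.* Pre-specify the variables in the weight model.

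This costs one sentence and weighting code of the kind already contemplated for dropout, with no new data. Precision falls slightly: a simulation at about 240 × 0.85 = 204 completers gave a standard error of about 1.65-1.68 for weighting, against 1.61-1.62 for intention-to-treat. The estimate would also depend on a weight model fitted with few co-intervention users: at the assumed 10-12%, 0.10 × 204 to 0.12 × 204, or about 20 to 25 women.
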